### **6.4 Method of statistical analysis**

The primary variable, change from baseline in number of signs and symptoms as observed in the video and detected from cardiorespiratory monitoring, will be analyzed using an analysis of covariance model (ANCOVA), taking the number of episodes at baseline as the covariate. The number of signs and symptoms at baseline, at the end of the study, change from baseline, and % change from baseline will be presented for the treatment comparison.

The secondary variables, including the number of symptomatic reflux episodes of GERD as observed from the video, together with reflux detected from pH/impedance, and GERD-related signs detected from cardiorespiratory monitoring associated with a reflux from pH/impedance monitoring, will be analyzed and presented in the same way as the primary variable.

Percent time of peaceful quietness, sleep, and crying will be summarized from video monitoring data for each patient separately, at baseline and at the end of the study. For each parameter (ie, % time of peaceful quietness, sleep, and crying) change from baseline in % time will be calculated. The comparisons between treatment groups in change from baseline will be made using ANCOVA taking baseline % time as the covariate. For each parameter, the % time at baseline, at the end of study, and change from baseline will be presented for evaluating the treatment difference.

Other GERD-related signs and symptoms (eg, gagging, back arching, irritability/crying/fussing, vomiting, apnea, bradycardia, oxygen desaturation) will also be assessed at baseline and at the end of the study via video and cardiorespiratory monitoring along with measurements from pH/impedance monitoring. The number of these events will be summed up for each patient at each time point for each sign and symptom individually or combined as appropriate. Change from baseline in number of events will be compared between treatment groups using ANCOVA, taking the baseline number of events as the covariate. Patients will also be categorized as 'having' or 'not having' the sign or symptom, individually or combined as appropriate. Difference between treatment groups in percentage of patients having no event will be compared using a chi-square test. Percentage of patients having no event at baseline as well as at the end of study will be tabulated for each treatment group separately.

The Physician's Global Assessment will be collected at baseline and at the end of the study. A CMH test stratifying on baseline severity will be used to compare the difference between esomeprazole and placebo in the percentage patients having no symptoms. A summary table of the percentage of patients having no symptoms at the end of the study will be presented by baseline severity for each treatment group separately.

Descriptive statistics will be provided on change from baseline in number of signs and symptoms, the primary efficacy endpoint, for various sub-groups if appropriate (eg, site, age group, days on study medication). Descriptive statistics will be provided on other efficacy endpoints of interest (eg, percentage of cardiorespiratory events, percentage of apnea resolution rates, percentage on vomiting categories, pharmacodynamic parameters).

Descriptive statistics will be provided for the evaluation of the safety profile (eg, AEs, lab parameters, vital signs).

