### **3. STUDY PLAN AND PROCEDURES**

#### **3.1 Overall study design and flow chart**

This Clinical Study Protocol has been subjected to a peer review according to AstraZeneca standard procedures.

This will be a multicentre, randomized double-blind, placebo-controlled study to evaluate the efficacy and safety of 0.5 mg/kg esomeprazole administered once daily for the treatment of symptomatic GERD in neonatal patients. Patient's size and medical condition must allow for performance of all study related procedures and administration of investigational product as judged by the investigator.

At the point of study entry, the patient will be an inpatient in the Neonatal Intensive Care Unit (NICU), special care nursery, or equivalent hospital ward and will be expected to remain an inpatient for the treatment period of the study. If the patient is discharged prior to completion of the treatment phase, patients may be given the option of having at home visits for study drug administration at the discretion of the investigators. These patients will need to be readmitted to the hospital for final study day procedures.

Patients will be enrolled at 3 centres located in Australia, Germany and the United Kingdom. Approximately 30 patients are expected to be randomized at each investigational site.

[Figure 1](#) presents the study flow chart. [Table 1](#) presents a study summary of scheduled assessments and procedures.

The signs and symptoms and other variables to be assessed may be divided into 3 groups, gastrointestinal, neurobehavioral and cardiorespiratory, and they are:

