A qualified reader, (either a central reader or site specific as applicable) per standard guidelines, will review the 8 hours of all the integrated data (cardiorespiratory monitoring, pH, impedance and video) and document any correlations between the events and the presence of reflux. The start and stop time of events will be determined so that durations can be calculated. The reader who will be reviewing the integrated data, as well as all site personnel, will be blinded to the investigational product assigned to the patient.

The 18 – 24 hour pH/impedance data will be used to calculate the reflux index in those patients that complete this procedure. However, as long as patients have completed the 8 hours of video monitoring, they will be considered evaluable regardless of whether they complete the remaining pH/impedance monitoring.

The following assessments of all types of reflux episodes (acid or non-acid) will be made at baseline and after treatment using standard reports from the pH/intraluminal impedance monitoring:

[figure not shown]
- acidic GER episodes (pH<4)

- weakly acidic GER episodes (pH 4 – 6.9)
- non acidic GER episodes (pH $\geq$ 7)
- liquid GER episodes
- mixed gas/liquid GER episodes
- mean bolus clearance time
- mean acid clearance time

The following assessments of acidic reflux episodes will be made at baseline and after treatment using the standard reports from the esophageal pH probe based on the entire time of pH monitoring:

- number of acidic reflux episodes (pH<4)
- number of acidic reflux episodes greater than 5 minutes
- % time pH < 4
- % time pH 4 – 6.9

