### **3.5 Method of assigning patients to treatment groups**

A preliminary identifying number (enrollment number) will be allocated to all patients at baseline, so that patients can be identified without making assumptions about their subsequent eligibility for the main study. Patients who do not meet the eligibility requirements for the treatment period will be considered screen failures and will keep their assigned identifying numbers.

Patient eligibility will be established before treatment randomization. Patients will be randomized strictly sequentially, as patients are eligible for randomization. If a patient discontinues from the study, the patient number will not be reused, and the patient will not be allowed to re-enter the study. If a number or a treatment is allocated incorrectly, no attempt should be made to remedy the error once study medication has been dispensed. The patient will continue with the allocated randomization code and corresponding clinical supplies. AstraZeneca or its designee should be notified as soon as the error is discovered.

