**Table 3 Study objectives and endpoints**

Objective	Endpoint	Summary statistic for analysis	Analysis method
Primary: to assess the difference between esomeprazole and placebo in the treatment of signs and symptoms of GERD as observed by 8-hour video and cardiorespiratory monitoring in neonatal patients	Primary: change from baseline in the number of occurrences of symptoms of GERD, as observed from video recording, and GERD-related signs detected from cardiorespiratory monitoring	Primary: mean change from baseline in symptomatic episodes by treatment group	Primary: ANCOVA, taking baseline number of episodes as a covariate, will be used for the treatment comparison

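### The primary ANCOVA names no centre term; adding centre as a fixed factor would be a low-priority, near-free gain in precision, possibly a very small one

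*Protocol*

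**What the plan says.** Section 6.4 states that the primary variable "will be analyzed using an analysis of covariance model (ANCOVA), taking the number of episodes at baseline as the covariate". Table 3 has the same model: "ANCOVA, taking baseline number of episodes as a covariate, will be used for the treatment comparison". The synopsis repeats it. Neither centre nor reader is named as a term in any of the three.

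On centres, section 3.1 says "Patients will be enrolled at 3 centres located in Australia, Germany and the United Kingdom" and "Approximately 30 patients are expected to be randomized at each investigational site".

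On how the count is produced, section 3.1.6 has site staff write surveillance notes and mark events in the pH/impedance data. The integrated recording is then reviewed by "A qualified reader, (either a central reader or site specific as applicable) per standard guidelines". Section 4.6.2.2 has the reader judge the events marked in this way.

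Site enters the analysis of the primary endpoint only through descriptive statistics "for various sub-groups if appropriate (eg, site, age group, days on study medication".

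On allocation, section 3.5 says "Patients will be randomized strictly sequentially, as patients are eligible for randomization". It does not say whether the list is balanced by centre.

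Section 6.1 leaves the analysis populations, missing data and derived variables to the SAP. Model terms are not on that list.

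**The concern.** With only three centres, each of useful size, a fixed centre effect is easy to estimate. There are also reasons to think that centre could matter: local marking of events, possibly local readers, and care given in three countries. If the change score differs by centre for reasons that the baseline count does not capture, a model without centre leaves those differences in the residual variance. The treatment effect is then estimated less precisely than it could be. If the randomisation list is balanced within centre, the standard error is also larger than the design warrants.

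What is at stake is precision and a few points of power. Section 6.5 says that no relevant historical data were available for the sample size, and power at 38 per arm is about 81.8%, so there is little to spare.

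**Working it through.** **Inputs.** Section 6.5 gives an SD of 1.5 times the treatment difference, 38 per group, at least 80% power and alpha 0.05. I take alpha as two-sided; a one-sided test would need only 28 per group, which does not fit. The protocol gives no figure for the share of variance due to centre, so every share below is an assumption.

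**1. The plan's own figure.** The noncentrality is (1/1.5)/√(2/n). The normal approximation needs 36 per group. The noncentral t gives 79.7% at 36, 80.8% at 37 and 81.8% at 38. The stated 38 per group for at least 80% power therefore holds, without a centre term.

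**2. Cost of the term.** At n = 38 the noncentrality is 0.6667/0.2294 = 2.906. Treatment and baseline leave 76 − 3 = 73 error degrees of freedom. Adding a three-level centre factor leaves 71. If centre explains nothing, power is 81.8% either way, a loss of about 0.03 percentage point.

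**3. Gain from the term.** Let R be the share of residual variance, after baseline adjustment, that centre explains. The standard error is multiplied by √(1 − R) and the noncentrality becomes 2.906/√(1 − R), with 71 df.

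| R (assumed) | SE factor | Noncentrality | Power with centre | Power without |
|---|---|---|---|---|
| 0 | 1.000 | 2.906 | 81.8% | 81.8% |
| 0.05 | 0.975 | 2.981 | 83.7% | 81.8% |
| 0.10 | 0.949 | 3.063 | 85.6% | 81.8% |
| 0.20 | 0.894 | 3.249 | 89.3% | 81.8% |

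This takes the planning SD to include centre variation.

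**4. How much of a stable centre difference is left after baseline.** Suppose that a centre or reader shift is equal at both visits. Let it make up a share s of the variance of each count, let r be the within-centre correlation between visits, and let the two visits have equal variances. The residual variance is 1 − (s + r(1 − s))² without centre and (1 − s)(1 − r²) with it. The ratio of the second to the first simplifies to (1 + r)/(1 + r + s(1 − r)). At an assumed r = 0.5:

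- s = 0.10: 1.5/1.55 = 0.968, so R is 3.2% and the SE falls 1.6%.
- s = 0.20: 1.5/1.60 = 0.938, so R is 6.3% and the SE falls 3.2%.
- s = 0.30: 1.5/1.65 = 0.909, so R is 9.1% and the SE falls 4.7%.

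Baseline thus removes roughly two thirds of a stable shift. It removes more at a higher correlation: at r = 0.7 and s = 0.10, R = 1 − 1.7/1.73 = 1.7%. It removes less at a lower one: at r = 0.3 and s = 0.20, R = 1 − 1.3/1.44 = 9.7%, about half. In simulations of an equal shift at r = 0.5, with s of 0.10 and 0.30, power differed by only 0.4 to 0.7 point. Power was above 93% in those runs, so the gap in points is compressed.

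**5. Validity of the test without centre.** Simulation used 76 infants, 3 centres and 4,000 runs per setting (Monte Carlo error about 0.3 point at a 5% level). The centre effect was placed on the change score only.

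| Centre share (assumed) | Type I error without centre, allocation balanced by centre | Type I error without centre, not balanced |
|---|---|---|
| 0.10 | 4.7% | 4.9% |
| 0.20 | 3.1% | 4.8% |
| 0.30 | 2.1% | 5.3% |

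No setting shows real inflation. Under balanced allocation the model without centre also has slightly more power than the 81.8% in step 3. At shares of 0.10 and 0.20, the simulated power goes from 83.7% to 86.6% and from 83.5% to 88.7% when centre is added. The gain is then nearer 3 and 5 points than 4 and 7.5.

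**The case against.** The strongest reply is that the model already deals with the likely mechanism. Local marking habits, a local reader and national practice are mostly stable features. The same procedures apply at baseline and on the final day, and the endpoint is a change score adjusted for baseline. Step 4 bears this out at moderate or high correlation. An R of 10% to 20% would generally need centre-specific change over the 14 days of treatment, or a weak correlation between visits, and the protocol gives no figure for either. A central reader remains possible, and readers are blinded and work to standard guidelines. This part of the objection stands, and it limits the point to a modest gain.

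A second reply is that the wording does not say baseline is the only term and that a SAP could add factors. This stands in part. But the model is given three times without centre, and section 6.1 does not list model terms among what the SAP will settle.

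A reader might go further and infer that omitting centre biases the treatment estimate, inflates the type I error or leaves the trial underpowered. The documents do not support this. Chance imbalance between centre and arm is ordinary sampling variation, which the standard error covers when allocation is not balanced by centre. When it is balanced, the test is conservative. The stated power is met without the term. A shortfall appears only if 1.5 times the difference is read as a within-centre SD (77.6% at an assumed centre share of 0.10), and section 6.5 does not say that.

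**Conclusion.** The point holds as a low-priority improvement. The protocol's primary model omits a recorded factor that could carry residual variance, and including it costs almost nothing. The consequence of the omission is some loss of precision, plus a conservative test if allocation is balanced by centre.

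The gain may be near zero. It reaches about 2, 4 or 7.5 points of power only if centre explains 5%, 10% or 20% of the variance left after baseline adjustment. Those shares are assumptions. The figures also rest on a two-sided test, 38 evaluable infants per arm and a planning SD that includes centre variation.

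**What to change.** In section 6.4, Table 3 and the synopsis, specify the primary ANCOVA with treatment, centre (fixed, three levels) and baseline count. Use the same terms in the secondary ANCOVAs, each with its own baseline. Make the change before unblinding, so that the choice cannot depend on the results.

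The cost is a line of text in each place and 2 degrees of freedom (73 to 71), which is under 0.1 point of power if centre explains nothing. The sample size need not change.

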## **4.2 Screening and demographic measurements**

Each patient will undergo a baseline assessment prior to study Day 1 (first day of study drug treatment). This will consist of:

- demographic data (date of birth, sex and race)
- medical history and documentation of normal ECG
- physical examination and vital signs - see [Table 5](#)
- laboratory screening (haematology, biochemistry and urinalysis)
- cardiorespiratory monitoring
- esophageal pH-monitoring
- intraluminal impedance monitoring
- video monitoring

Data listed above are to be recorded in the eCRF at the pre-entry visit.

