### **6.2 Description of outcome variables in relation to objectives and hypotheses**

The primary objective of this study is to evaluate if there is a difference between esomeprazole and placebo in the treatment of signs and symptoms of GERD as observed in an 8-hour video recording along with cardiorespiratory monitoring. Video, pH/impedance, and cardiorespiratory monitoring will occur at baseline (before treatment) and the final study day. Symptoms or symptomatic reflux episodes of GERD will be determined by a qualified reader, in a blinded fashion, by review of the video recording, the pH/impedance monitoring, and the cardiorespiratory monitoring. Other variables can be found in [Table 3](#).

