## **6.5 Determination of sample size**

No relevant historical data on symptomatic episodes in this patient population was available for the sample size calculation. It was assumed that the standard deviation is about 1.5 times greater than the difference between treatment groups in number of symptomatic episodes.

Under the assumption, it would need 38 patients per group to provide at least 80% power at alpha of 0.05 to detect a difference between esomeprazole and placebo in change of symptomatic episodes from baseline.

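### The primary ANCOVA adjusts for the baseline count alone; a pre-specified age covariate could add some precision at almost no cost

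*Protocol*

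**What the plan says.** Section 6.4 states that the primary variable, change from baseline in the number of signs and symptoms, "will be analyzed using an analysis of covariance model (ANCOVA), taking the number of episodes at baseline as the covariate". The primary row of Table 3 agrees: "ANCOVA, taking baseline number of episodes as a covariate, will be used for the treatment comparison". The synopsis repeats the same model. The baseline count is thus the only covariate named, in three places.

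Age appears once in relation to the primary endpoint. Section 6.4 allows descriptive statistics "for various sub-groups if appropriate (eg, site, age group, days on study medication"). Section 3.5 describes sequential randomisation and mentions no stratification by age.

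The population is wide in age. The synopsis and inclusion criterion 2 give 28 to 44 weeks, and the synopsis adds infants up to 1 month corrected age. Section 4.2 lists "demographic data (date of birth, sex and race") and does not list gestational age at birth.

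Section 6.5 sets the sample size: "it would need 38 patients per group to provide at least 80% power at alpha of 0.05 to detect a difference". It assumes that "the standard deviation is about 1.5 times greater than the difference between treatment groups in number of symptomatic episodes", and says of the basis: "No relevant historical data on symptomatic episodes in this patient population was available for the sample size calculation".

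**The concern.** In a small randomised trial, a baseline variable that predicts the outcome beyond the baseline count shrinks the residual variance when it is in the model. Left out, its contribution stays in the error term. Age is a natural candidate here. The infants range from very preterm to past term, and the counted events include apnea, bradycardia, desaturation and vomiting. The baseline count will carry part of any age effect, but it comes from a single recording of about 8 hours, of which about 6 need be evaluable (section 3.1.6), so it is likely to be a noisy measure.

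At stake is precision in one primary test with a modest power margin and an SD assumption that had no data behind it. Neither the randomisation nor the model accounts for age. If the arms happened to differ in age, an adjustment introduced after unblinding would look post hoc.

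**Working it through.** **Inputs**
- From section 6.5: alpha 0.05, 38 per group, SD = 1.5 × difference, so difference/SD = 1/1.5 = 0.667.
- Assumed: a two-sided test. Section 6.5 does not state sidedness, but the objective in section 6.2 is to "evaluate if there is a difference between esomeprazole and placebo", which has no direction.
- Assumed: the section 6.5 SD is the residual SD after the baseline count.
- Assumed: R², the share of that residual variance explained by age, is 0, 0.05, 0.10 or 0.20. The documents give no value.

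**Step 1: reproduce the plan's figure.** The normal approximation needs 36 per group and the t-test 37. Power at 38 per group is 82.8% (normal) or 81.8% (noncentral t). The stated 38 for at least 80% power is confirmed. Other readings do not give 38: a one-sided test needs 28, and an SD of 2.5 times the difference needs 99.

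**Step 2: add age.** The residual SD becomes 1.5 × √(1 − R²) times the difference. The noncentrality is

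λ = (1/1.5) × √(38/2) / √(1 − R²) = 2.906 / √(1 − R²).

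Degrees of freedom are 76 − 3 = 73 with the baseline count alone, and 76 − 4 = 72 with age added.

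| Model | R² of age | λ | Power (t) | Confidence interval width factor | Equivalent n per arm, 38/(1 − R²) |
|---|---|---|---|---|---|
| Baseline count only | – | 2.906 | 81.8% | 1 | 38 |
| Plus age | 0 | 2.906 | 81.8% | 1.00 | 38.0 |
| Plus age | 0.05 | 2.981 | 83.7% | 0.975 | 40.0 |
| Plus age | 0.10 | 3.063 | 85.6% | 0.949 | 42.2 |
| Plus age | 0.20 | 3.249 | 89.3% | 0.894 | 47.5 |

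In the second row the lost degree of freedom moves power from 81.79% to 81.78%, about 0.01 point.

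**Step 3: chance imbalance.** The difference in mean age between arms has standard error √(2/38) = 0.23 SD of age. About 1 trial in 20 would therefore differ by more than 1.96 × 0.23 = 0.45 SD. If R² = 0.10, that shifts the estimate by √0.10 × 0.45 = 0.14 residual SD. Against an assumed effect of 0.667 SD this is 0.14/0.667, or about 21%.

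**The case against.** The strongest reply is that nothing here is wrong. ANCOVA on the baseline count is unbiased under randomisation, and its type I error already allows for chance imbalance in age. The power calculation claims no benefit from age, and 38 per group delivers more than 80% without it. All of this stands.

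It is also true that the age–outcome link is assumed. No section says that the counted signs change with postmenstrual age over 10 to 14 days. The nearest figures, in section 1.1, are daily regurgitation in 50% of infants at 0 to 3 months and 67% by 4 to 6 months, which extend well beyond this trial's age range. The baseline count may absorb most of any age effect, and the remaining R² could be close to zero.

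A reader might infer a stronger case from Appendix C: Table 2 there shows predicted AUC/AUC50 at 0.5 mg/kg falling from 27 at 5 days to 6 at 30 days for a 1 kg infant. The documents do not support using this for a postmenstrual age covariate, for three reasons.
- The model's age term is time after birth, and Appendix C section 4.3.1 describes enzyme maturation as independent of gestational age.
- Exposure varies only in the active arm. That bears on an age-by-treatment interaction, not on a main effect.
- The modelled response is nearly flat over this range. With equation 3 and exponent 1.43, 27^1.43/(1 + 27^1.43) is about 99% acid inhibition and 6^1.43/(1 + 6^1.43) about 93%.

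Finally, criterion 2 may already mean age at entry, in which case adding postnatal age to that figure would count it twice. The fix has to settle this.

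**Conclusion.** The point holds as a low-severity efficiency improvement. The protocol fixes the baseline count as the sole covariate in a population of wide age range, so some precision may be lost. If age explains 5% to 20% of residual variance, the gain is roughly 2 to 8 points of power, equivalent to about 2 to 9 more infants per arm. If age explains nothing, the cost is about 0.01 point. These figures rest on the assumed R², a two-sided test and the plan's own SD-to-difference ratio.

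Two stronger readings should be avoided. One is that precision is definitely being lost; with no age–outcome correlation in the documents, that is possible but not shown. The other is that the primary comparison is biased or underpowered; it is neither. The imbalance figure in the working describes what could happen in a single realised trial, and is not a bias on average.

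**What to change.** Before unblinding, name postmenstrual age at baseline (continuous, in weeks) as a second covariate in the primary ANCOVA and the matching secondary ANCOVAs, in section 6.4, Table 3 and the synopsis. The statistical analysis plan should carry the same wording.

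State the derivation: gestational age at birth plus postnatal age. Clarify whether the 28 to 44 weeks in inclusion criterion 2 refers to age at birth or at entry, so that postnatal age is not counted twice. Add gestational age at birth to the demographic data in section 4.2 and to the eCRF. Date of birth is already collected, and gestational age has to be known to apply criterion 2.

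The cost is one phrase in three places, one data field and one degree of freedom. No new measurement on the infant is needed.
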